The primary objective of this study is to identify whether electroacustimulation is a beneficial anesthesia adjunct in children undergoing procedures on their congenital heart defects. Does it decrease myocardial injury and or need for myocardial support. Differences between the groups Troponin I levels pre-operative and six hours postoperative will be evaluated.

Secondary Objectives:

1) Evaluate the incidence discomfort in the post- operative period.

To evaluate the incidence and severity of pain assessed by using age appropriate West Virginia University Hospital approved nurse guided pain scoring the Neonatal/Infant Pain Scale (NIPS) (children age birth to 2 months) FLACC (2 months to 7 years or unable to communicate, or VAS(age 8-18) every 2 hours for 48 hours post procedure.

2) Determine the incidence of Acute kidney injury (AKI) between these two treatment groups. Acute Kidney Injury will be evaluated by AKIN criteria. Creatinine and urines will be measured at 6, 12, 24 and 48 hours after bypass.

Need for post-operative myocardial support:

To assess the need for myocardial support an inotropic score will be used and compared between the two groups. The Inotropic score will be evaluated every 6 hours for 48 hour between the 2 groups

Study Design:

This is a single site, randomized, blinded, sham controlled, parallel group study to identify whether electroacustimulation is a beneficial anesthesia adjunct in children undergoing procedures on their congenital heart defects.

Study subjects age's birth to eighteen years, undergoing cardiac surgery for their congenital heart lesions will be considered for entrance into the study. The randomized subjects will receive either electrostimulation or sham during their surgery for CHD. Subjects are expected to remain in the hospital 48 hours post procedure. Standard of care blood samples will be obtained pre-operative and post-operative. The only study specific blood sample will be Troponin I levels which will be obtained presurgically after the lines have been placed and a 6 hours post bypass/aortic clamp removal. Urine samples will be obtained pre-surgically after placement of the Foley and every 6 hours post bypass for 48 hours while the Foley catheter is still in place .

Number of Subjects planned:

Approximately 108 patients, over the two years, with randomization of 54 allocated to each group.

- Electroacustimulation (treatment) frequency will be at 2Hz and 100 Hz the amplitude will be 1000mA.

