Group 2: Receive sham electroacustimulation (control) will not have stimulation. Subjects will undergo procedures on their congenital heart defects.

Blind:

The anesthesia provider will be blinded as to whether the electroacustimulation device is actually turned on or not. The research coordinator will hold the blind. The electroacustimulation machine will be placed in an opaque bag to secure the blind. The current is below the threshold to stimulate the muscle so that no movement will be visible. It is also below the sensory threshold so that it will not produce any discomfort in the subjects.

Stimulation/Sham will be continued until the patient is ready for transport to the PICU.

Post-Operative: PICU

Stimulation/Sham will be discontinued.

PICU care givers will be blinded as to which group the patients were randomized.

Subject comfort will be assessed using age appropriate West Virginia University Hospital approved nurse guide pain scoring based on Universal Pain Assessment Tool or the Neonatal/Infant Pain Scale (NIPS) will be recorded in the electronic medical record (EMR) every 6 hours for 48 hours.

The amount of opiate infused, Nausea, Vomiting, and urine output will be assessed every 6 hours for the first 48 hours and recorded in the EMR.

Research blood samples for troponin I will be obtained at 6 hours post surgery. Total amount of 7cc of blood will be

obtained for this study. WVUH lab will process samples.

Research urine samples (.05-2cc) will be collected at 6, 12, 24, and 48 hours after bypass. The urine samples will be stored in a -80 degree freezer and analyzed by ELISA testing at the end of the study for Superoxide dismutase, Neutrophil gelatinase – associated lipocalin (NGAL), WNT4.

AKIN criteria will be used to evaluate AKI every 6 hours. Inotropic score will be recorded every 6 hours.

Daily chest x-ray will be used to assess pulmonary status.

The AKIN criteria, inotropic scores, chest x-ray and creatinine levels, (used for AKIN), are standard of care measurements and the data will be collected for this research project.

An Electrostimulation Documentation Guide has been developed for the staffing. (Appendix A2)

Tool/Instruments to be used in data collection:

Tools and instruments for data collection: secured Excel data base; Neonatal/Infant Pain Scale (NIPS); AKIN stage; Inotropic Scores; RACHS categories (Appendix A3-6).

Variables:

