To address the overall difference between the control and the acupuncture group, we will look at the score changes between baseline and 48 hours. For the continuous outcomes, a t-test based on the difference in outcome will be used to compare the two treatment groups. For the categorical outcomes, a logistic regression model (generalized linear model with binary or multinomial outcome) will be used to compare the two treatment groups' at baseline and 48 hours. The generalized linear hypothesis methodology will be used to contrast the two time points. This approach will provide consistency of modeling methodology for the secondary analyses. Adjusted models will be considered (e.g. glm regression with identity and/or logit links) to account for any data imbalances, potential confounders, etc. Minimally, a RACHS score adjustment will be assessed for its relevance.

A secondary analysis will be used to describe the longitudinal (repeated measures) outcome trends. A generalized linear mixed-effects regression model will be used for longitudinal data. Both unadjusted and adjusted trends will be assessed. We will account for both heteroscedasticity and autocorrelation variance-covariance structures. The generalized linear model approach will permit trend characterizations for either continuous or categorical outcomes under the same generalized linear model framework.

[figure not shown]
All results, predicated on formal hypothesis testing methodology, will use an alpha-level of 0.05 for statistical significance. Bonferroni or Scheffe adjustments will be used, when appropriate, to retain the family-wise alpha level of 0.05 when performing multiple tests under the same global hypothesis or construct. Every effort will be used to ensure all relevant information is collected. In the event of missing data, generalized estimating equations for longitudinal analysis will be used. All statistical analysis will be done using the most recent version of the R language for statistical computing and graphics.

Tentative time table: Approximately 2 years to enroll 108 subjects.

[figure not shown]
References:

- 1) Instruction manual for KWD-808I Multipurpose health device, Ying Di page 21.
http://www.ib3health.com/products/Acupunctoscope/KWD808_I.asp#808I_Instruct [Accessed Sept. 5, 2016]

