Appendix B: Variable descriptions.

Variable	Description	Measurement times	Measurement scale
Outcomes			
Pain score	Age appropriate WVUH approved Nurse guided pain scoring. The pain scale score will be recorded in the electronic medical record.	Every 2 hours for 48 hours	Tool: NIPS score, FLACC score or Visual analog scale Scale: 0-10; 0=none, 10=worst pain
Inotropic score	IS or VIS 1 st 24 hours IS or VIS 24-48 hours	Every 6 hours for the first 48 hours of observation	Group 1-5
Narcotic use	Opiate use will be its own variable as well as a surrogate for pain as comfort will be maintained at a score less than 40% of the max possible score for the pain scoring system used.	Every 2 hours for 48 hours	mcg/kg/hr
Creatinine/Urine	Assessment of AKI-renal complication	Baseline, 6, 12, 24, and 48 hrs post CPB	Creatinine mg/dl Urine ml/kg/hr
Neutrophil gelatinase-associated lipocalin (NGAL)	Renal biomarker-urine sample collected and frozen-renal complication	Baseline, 6, 12, 24, and 48 hrs post CPB	ELIZA
WNT4	Renal Biomarker-urine sample collected and frozen-renal complication	Baseline, 6, 12, 24, and 48 hrs post CPB	ELIZA
AKIN score	Acute kidney injury (AKI)-renal complication	Every 6 hours for the first 48 hours of observation (EMR)	Stage 1-3
Superoxide dismutase	Renal Biomarker-urine sample collected and frozen-cardiac injury-complication	Baseline, 6, 12, 24, and 48 hrs post CPB	ELIZA
Pneumonia	complication	Daily (Chest x-ray)	Indicator: 0=No, 1=Yes
Intubation time	The date and time of intubation as part of surgery prep.	Obtained from patient's EMR	Date and time
Extubation time	The date and time of extubation as part of surgery prep.	Obtained from patient's EMR	Date and time
PICU arrival	The date and time of arrival in the PICU	Obtained from patient's EMR	Date and time
PICU discharge	The date and time of discharge from the PICU	Obtained from patient's EMR	Date and time
Other variables			
Age	Age of the patient	Baseline	In days
Sex	Sex of the patient	Baseline	Indicator: 0=Male, 1=Female
Cardiac defect	Type of CD	Baseline	Diagnosis

Cyanosis	Blueness of skin- based on room air oxygen level less than 90% sat-guide for opiate amount-complication	Baseline	1=yes 2=no
RACHS score	Randomization Guide	Baseline	Categorical: 1 through 6
CPB start time/ Aortic clamp time	Cardiopulmonary bypass (CPB) start time/ Placement of aortic clamp	Obtained from patient's EMR	Date and time

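### The SAP's one rule for continuous outcomes, a t-test on baseline-to-48-hour change, conflicts with the sampling schedule for troponin I, narcotic use and pain, and no model is named as primary

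*Combined protocol and SAP*

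**What the plan says.** The Statistical analysis plan describes the overall comparison in these terms: "we will look at the score changes between baseline and 48 hours". It continues: "For the continuous outcomes, a t-test based on the difference in outcome will be used to compare the two treatment groups". No outcome is exempted and no other time point is given.

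On covariates it says "Adjusted models will be considered (e.g. glm regression with identity and/or logit links) to account for any data imbalances, potential confounders, etc", then "Minimally, a RACHS score adjustment will be assessed for its relevance". It gives no criterion, no closed covariate list, and no statement of whether an adjusted result may replace the t-test.

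Other sections are more specific. The Primary Objective states: "Differences between the groups Troponin I levels pre-operative and six hours postoperative will be evaluated". Post-Operative: PICU has one later draw: "Research blood samples for troponin I will be obtained at 6 hours post surgery". Duration of Treatment limits follow-up for myocardial injury to 6 hours. Sample size uses a morphine-equivalent dose in mg/kg and a two-sided unequal-variance t-test. Appendix B lists narcotic use in mcg/kg/hr, recorded through 48 hours without a baseline, and describes it thus: "Opiate use will be its own variable as well as a surrogate for pain". Pain score has no baseline there either.

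**The concern.** An analyst who follows the SAP literally has no 48-hour value for the measure under the primary objective and no baseline for the variable that set the sample size. Some other analysis must be used for both. The documents point to candidates, but the SAP does not adopt them.

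The adjustment decision is open in the same way. Several analyses of one outcome would fit the text, and none is designated as the result on which the trial is judged. A reader of the final report could not tell whether the model was chosen before or after the results were seen.

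**Working it through.** **1. The plan's own sample size.** Inputs from Sample size: means 0.71 and 0.57 mg/kg (difference 0.14), SDs 0.3 and 0.2, 54 per arm, two-sided alpha 0.05.

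- Standard error = √(0.3²/54 + 0.2²/54) = √(0.13/54) = 0.0491
- Noncentrality = 0.14/0.0491 = 2.853; Welch df = 92.3; power = 80.6%
- At 53 per arm power is 79.9%, so 54 is the smallest sufficient number.

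The figure reproduces. It is for a plain comparison of dose between arms, with no change score.

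**2. The rule against the measurement schedule.**

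| Outcome | Baseline | 48 hours | Change computable? |
|---|---|---|---|
| Troponin I | Pre-operative | None (last draw at 6 h) | No |
| Narcotic use | None | Yes | No |
| Pain score | None | Yes | No |
| Creatinine, NGAL, WNT4, superoxide dismutase | Yes | Yes | Yes |

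The last row follows from Appendix B: "Baseline, 6, 12, 24, and 48 hrs post CPB". Setting baseline opiate to zero does not rescue the rule for narcotic use. The change would then be the rate at 48 hours in mcg/kg/hr, not the mg/kg dose used for sizing.

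**3. What an open choice of model could cost.** The documents give no R² for the covariates, so R² is assumed. In simulated trials of 54 per arm with no treatment effect:

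- Better of an unadjusted and one adjusted test: type I error about 5.6–5.8% at R² = 0, and 6.5–8.6% across R² 0.1–0.5 (range over separate simulation runs).
- Fixed gate (adjust only if RACHS has p < 0.05): 5.2–5.4%.

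**4. What covariates could add for narcotic use.** Take three RACHS groups plus age (k = 3 terms). The root-mean-square SD is √((0.3² + 0.2²)/2) = 0.255. With conventional errors, noncentrality = (0.14/0.255)·√27 / √[(1 − R²)(1 + k/(105 − k))], on 106 − k df. The HC2 column is from 20,000 simulated trials per setting.

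| Assumed R² | Formula | Simulated, HC2 errors |
|---|---|---|
| 0 | 79.6% | 79.1–79.7% |
| 0.10 | 83.6% | 83.1% |
| 0.20 | 87.6% | 87.0–87.4% |
| 0.30 | 91.5% | 90.8–91.2% |

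Type I error with HC2 is 4.8–5.1%.

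**5. ANCOVA against a change t-test for troponin I.** Let ρ be the correlation between pre-operative and 6-hour values and s the ratio of the 6-hour to the pre-operative SD. Neither is in the documents. The variance ratio, ANCOVA to change, is s²(1 − ρ²)/(1 + s² − 2ρs). For example, s = 2 and ρ = 0.5 give 4 × 0.75/3 = 1.00. The power column assumes an effect for which the pre-operative-to-6-hour change test has 80% (noncentrality 2.827). The ANCOVA has the pre-operative value plus RACHS and age, the last two adding nothing (k = 4).

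| s | Variance ratio at ρ = 0.3, 0.5, 0.7 | ANCOVA power |
|---|---|---|
| 1 | 0.65, 0.75, 0.85 | 92.6%, 88.7%, 84.6% |
| 2 | 0.958, 1.000, 0.927 | 80.1%, 78.4%, 81.4% |
| 5 | 0.989, 0.893, 0.671 | 78.9%, 82.8%, 91.8% |

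The effect runs from a loss of about 2 points (78.4 against 80) to a gain of about 13 (92.6 against 80). Any gain here comes from the pre-operative value. With that covariate alone (k = 1), the same formula gives 79.6–93.3%.

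**The case against.** The strongest reply is that the analyses are not missing. The Primary Objective names the two troponin times, and a t-test on that change can be computed. Sample size names a quantity and a test for opiate dose. This stands: the defect is mainly a conflict between sections, and what the documents leave out is the opiate time window, a pain summary and the link from the SAP to those statements. A reader might infer that the primary measure cannot be analysed at all; the documents do not support that.

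A second reply is that naming one unadjusted Welch test would close the model gap equally well, so ANCOVA with RACHS and age is a preference. This also stands. The t-test is valid, and every R², correlation and SD ratio above is assumed. A reader might infer that the trial is underpowered without adjustment, but on its own inputs it reaches 80.6%.

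Third, the plan never says it will choose by result. Assessing the relevance of RACHS is closest to a gate, which is nearly harmless. So the 6.5–8.6% illustrates what the wording leaves possible; it is not an estimate of this trial's type I error.

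A reader might also infer from the Appendix B label Randomization Guide that RACHS was a stratifier which the analysis ignores. Treatment Groups, Study Procedures and Randomization name no strata, so the documents do not settle this.

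**Conclusion.** The concern holds as a conflict between the SAP's single change rule and the measurement schedule, together with an undesignated primary model. Both parts rest on the text alone. They affect the measure under the primary objective, the sizing variable and pain score. The rule works for creatinine and the three urine biomarkers. The plan should be changed, although the Sample size section calls this a pilot study and its calculation is sound.

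The possible rise in type I error (to about 5.6–5.8% at R² = 0, or 6.5–8.6% at R² 0.1–0.5) depends on assumed covariate strength and on a selection that the plan does not announce. Any precision gain from RACHS and age depends wholly on assumed values: morphine power of about 83–91% at R² 0.10–0.30, and about 1 point lost at R² = 0.

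**What to change.** Replace the single rule with one analysis per outcome. Date it and sign it off before anyone analysing sees outcomes with allocation. Waiting only for the cross-walk file is a weak safeguard, because the project statistician generates the allocation list.

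- **Troponin I:** the 6-hour value, adjusted by ANCOVA for the pre-operative value. State one time origin, since Study Design counts from bypass or clamp removal and Post-Operative: PICU from surgery. Add troponin I to the variable list, the Acupuncture Study Documentation Guide and Appendix B, where it is absent.
- **Narcotic use:** cumulative mg/kg over one stated window (for example 0–48 hours), compared between arms without a change score.
- **Pain score:** one post-operative summary (for example the mean over 48 hours), without a change score.
- **Creatinine, NGAL, WNT4, superoxide dismutase:** the 48-hour value adjusted for baseline.

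Use HC2 standard errors, because Sample size assumes unequal SDs. Fix any transformation on pooled blinded data. State that Mann-Whitney results, and unadjusted Welch results where the primary model is adjusted, are sensitivity analyses that cannot replace the primary one.

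As an option, add RACHS (collapsed, for example 1–2, 3, 4–6) and age to the models, with the form of age fixed in advance (for example log age).

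Separately, reconcile the Randomization Guide label with the randomization text. If RACHS was a stratifier, say so and keep it in the model.

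The cost is SAP wording, entries for troponin I in three lists, and one clarification. No extra patients or samples are needed. If RACHS and age are included but not prognostic, about 1 point of morphine power is lost.

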Predicated on the primary aim, the sample size for this pilot study we used a two-sided two-sample t-test with unequal variance t-test with an alpha level of 0.05 and power of 80%. A morphine equivalent dose of 0.71 mg/kg was used for the control group and 0.57 mg/kg for the acupuncture group. This represents a conservative 20% change between the control and acupuncture group. The standard deviation of the control group was estimated to be 0.3 mg/kg for the control group and 0.2 for the experimental group. **The total estimated sample size is 108 patients, over the two years, with 54 allocated to each group.** Historically, we would have had a potential enrollment and retention of approximately 74 patients per year accounting for a 25% non-consent rate and a 2% drop-out rate. This project is well powered for statistical significance and feasibility for a 2-year study.

Data collection:

The data will be retrieved from the EMR and imported or entered into a secured EXCEL database.

Statistical analysis plan:

For all aims, univariate statistics (e.g. mean, median, standard deviation, min, max and skew) will be used to describe the collected data. Parametric approaches (e.g. t-test, Pearson's correlation, and chi-squared test) will be used when the data satisfy the required statistical assumptions; they will be used to compare the demographic and clinical characteristics between treatment and control. If the distributional assumptions are untenable, then the Mann-Whitney test, Spearman

correlation, and Fisher's exact test will be used. We will use the Box-Cox or the exponential transformation when the absolute value of skew is greater than 0.4.

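### For tests of separate outcomes between two arms, Holm should replace the choice of Bonferroni or Scheffe, and the primary test should be stated as unadjusted at two-sided 0.05

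*Combined protocol and SAP*

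**What the plan says.** The Statistical analysis plan section sets 0.05 for all formal tests and adds that "Bonferroni or Scheffe adjustments will be used, when appropriate, to retain the family-wise alpha level of 0.05" when several tests address one overall hypothesis or construct. It does not list the constructs, count the tests in each, choose between the two methods, or say whether a primary test is exempt.

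The Sample size section rests on one comparison of opioid dose, using a "two-sided two-sample t-test with unequal variance t-test with an alpha level of 0.05 and power of 80" per cent. For the means, the input is: "A morphine equivalent dose of 0.71 mg/kg was used for the control group and 0.57 mg/kg for the acupuncture group". Next, for the spread, it is: "The standard deviation of the control group was estimated to be 0.3 mg/kg for the control group and 0.2 for the experimental group". From these follows the planned size: "The total estimated sample size is 108 patients, over the two years, with 54 allocated to each group".

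Two other places bear on what counts as one construct. The Narcotic use row of Appendix B says: "Opiate use will be its own variable as well as a surrogate for pain". The Primary Objective section asks: "Does it decrease myocardial injury and or need for myocardial support", and then names troponin I. The Sample size section nevertheless says that its opioid calculation follows from the primary aim.

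**The concern.** A multiplicity rule should use a method that holds the family-wise error for the tests it covers, at the least cost in power. Here the covered tests would mostly be different outcomes, each compared between the same two arms. Scheffe was designed for many contrasts within one model, so it is doubtful that it does anything across separate outcomes. Bonferroni does control the error, but a uniformly better procedure with the same guarantee exists.

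The sample size also spends the whole 0.05 on the opioid test. If the rule were later taken to cover that test, the stated 80% would no longer describe the analysis. An opioid p-value of 0.03, for example, would be significant if that test stands alone. It would not be if Bonferroni were applied over two tests. The plan does not say which applies, or that this must be settled before unblinding.

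**Working it through.** **1. Reproduce the plan's sample size.** Inputs from the Sample size section: difference 0.71 − 0.57 = 0.14 mg/kg; SDs 0.3 and 0.2; 54 per arm; two-sided alpha 0.05; unequal-variance t-test.

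- Standard error = √(0.3²/54 + 0.2²/54) = √(0.13/54) = 0.0491.
- Noncentrality = 0.14/0.0491 = 2.853.
- Satterthwaite degrees of freedom = 53 × (0.09 + 0.04)²/(0.09² + 0.04²) = 92.3.
- Critical t at 0.05 = 1.986. Power from the noncentral t distribution = 80.6%.
- At 53 per arm the power is 79.9%. So 54 per arm is the smallest number that reaches 80%, and 108 is reproduced exactly. Nothing is held back for multiplicity.

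**2. Scheffe for one outcome, two arms.** The Scheffe critical value is √[m × F(0.95; m, df)], where m is the dimension of the contrast space.

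- Two arms give m = 1. With 106 degrees of freedom (108 − 2), √F(0.95; 1, 106) = 1.983.
- The ordinary two-sided t value, t(0.975; 106), is also 1.983.

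The two are the same number. Using Scheffe separately for each outcome therefore leaves every test at 0.05, however many outcomes share the construct. With two independent outcomes the family-wise error would be 1 − 0.95² = 9.8%. Independence is an assumption made only for this illustration.

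**3. Bonferroni over two tests.** Suppose, as an assumption, that opioid dose and pain score form one comfort construct. Each is then tested at 0.05/2 = 0.025.

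- Critical t at 92.3 degrees of freedom = 2.279. Power of the opioid test at 54 per arm = 71.7%.
- To return to 80% would take 65 per arm (130 in total).

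**4. Holm over the same two tests.** The smaller p-value is compared with 0.025. If that test is rejected, the larger is compared with 0.05. The opioid test is rejected if its p-value is at most 0.025, or if it lies between 0.025 and 0.05 and the pain p-value is at most 0.025. Hence

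power(Holm) = 71.7% + Pr(opioid p in (0.025, 0.05] and pain p ≤ 0.025).

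The added term is between 0 and 80.6 − 71.7 = 8.9 percentage points. Holm power for opioid dose therefore lies between 71.7% and 80.6%. Its exact value depends on the power of the pain test and on how the two outcomes are related, and the documents give neither. Holm rejects whatever Bonferroni rejects, and it holds the family-wise error at 0.05 under any dependence between the tests.

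**The case against.** The strongest reply is that the rule can be read sensibly as it stands. The Sample size section ties its test to the primary aim. One primary test at 0.05, with adjustment only where a construct holds several tests, fits the wording and keeps both the power and the error control. The rule also commits to a family-wise 0.05, so a method that cannot deliver it would not be appropriate in that setting. This stands as a permissible reading, but the text does not state it.

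It is also fair that Scheffe is not always idle. The plan includes contrasts over time and repeated-measures models, where the contrast space can have more than one dimension. With two dimensions the Scheffe critical value is about 2.49 (93 degrees of freedom), and the opioid test would have about 64% power, which is stricter than two-test Bonferroni. The result in step 2 applies only to separate outcomes compared between two arms.

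A reader might infer that the plan itself puts the opioid test in a family, so that the 80% is already lost. The documents do not support that. The Appendix B sentence also calls opioid use a variable in its own right, and the Variables section lists it apart from the pain score. A reader might also posit a larger family containing opioid dose, but no third member is identified. The injury-and-support pairing in the Primary Objective does not include opioid dose and cannot lower its power. Nor does it help to treat every listed outcome as one unadjusted, independent family. The rule works by construct, and some outcomes are plainly related: AKIN staging, for instance, uses creatinine.

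**Conclusion.** The point holds as a better choice of method. For several outcomes compared between two arms, Scheffe adjusts nothing (1.983 against 1.983), and Bonferroni gives up power that Holm can keep at the same family-wise 0.05. The possible loss for the opioid test is 8.9 percentage points, from 80.6% to 71.7%. It arises only if that test is placed in a two-test family with the pain score and Bonferroni is used. That grouping is plausible but unstated.

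It would be going too far to say that the rule must either destroy the power or give no protection. An unadjusted primary test with adjustment among secondary outcomes avoids both, and the present wording allows it. The power figures rest on the plan's own means and SDs. They say nothing about troponin I, for which the documents give no effect size or SD. This is a cheap improvement, not a fault that must be fixed before the trial can be interpreted.

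**What to change.** Amend the Statistical analysis plan section as follows.

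1. Name the single primary test and state that it is made at two-sided 0.05 without adjustment. Bring the Primary Objective and Sample size sections into line on which outcome that is.
2. Replace the choice of Bonferroni or Scheffe with Holm for multiple outcomes within a named secondary construct. If opioid dose is secondary, one example is comfort, with opioid dose and pain score as its members.
3. Keep Scheffe, if it is wanted at all, only for multiple contrasts within one model.
4. If opioid dose is not the primary test and sits in a two-test Holm family, restate its power in the Sample size section as between 71.7% and 80.6%, depending on the power of the pain test.

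The cost is a few sentences, with no extra patients or data. Holm does not yield simple simultaneous confidence intervals, so intervals for the secondary outcomes would be reported unadjusted and labelled as such. The stated power may also look slightly less favourable.

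### The plan turns to unweighted GEE when data are missing, a weaker method in that case than the mixed model it already plans

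*Combined protocol and SAP*

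**What the plan says.** All of the modelling text is in the Statistical analysis plan of the combined document. The main comparison uses change from baseline to 48 hours: "For the continuous outcomes, a t-test based on the difference in outcome will be used to compare the two treatment groups". The longitudinal analysis ranks below it: "A secondary analysis will be used to describe the longitudinal (repeated measures) outcome trends". Its model is named next: "A generalized linear mixed-effects regression model will be used for longitudinal data". That paragraph adds that unequal variances and autocorrelation will be accounted for. Two sentences after the multiplicity rule comes the only missing-data provision: "In the event of missing data, generalized estimating equations for longitudinal analysis will be used".

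Urine collection is described in two ways. Study Design has samples taken "every 6 hours post bypass for 48 hours while the Foley catheter is still in place". The Post-Operative: PICU section says research urine "will be collected at 6, 12, 24, and 48 hours after bypass", with no catheter condition. The Labs table of the Documentation Guide and Appendix B give the same four post-bypass times, also without it. The frozen samples are to be "analyzed by ELISA testing at the end of the study for Superoxide dismutase, Neutrophil gelatinase"-associated lipocalin (NGAL) and WNT4. Other repeated outcomes carry no catheter condition; for example, "Inotropic score will be recorded every 6 hours".

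**The concern.** The two methods differ most when readings are missing. A mixed model fitted by maximum likelihood, if correctly specified, stays valid when the chance of a missing reading depends on values already observed (missing at random, MAR). Unweighted GEE in general needs missingness unrelated to the outcome (missing completely at random, MCAR). The plan holds the first method and names the second for the situation in which the first is the safer.

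For binary or multinomial outcomes the methods also estimate different quantities. The mixed model gives a subject-specific odds ratio and GEE a population-average one. Under the rule, the presence of a missing value decides which is reported.

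The urine biomarkers are where this could matter most. If samples end with the catheter, and the catheter comes out sooner in children who are doing better, the 48-hour readings come from a selected group.

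**Working it through.** **1. Will the rule be triggered?** No threshold is given. Pain alone is scheduled every 2 hours for 48 hours in Secondary Objectives and Appendix B: 48/2 = 24 readings, and 24 × 108 = 2,592. At the 6-hourly interval in the PICU section it is 48/6 = 8, and 8 × 108 = 864. The Sample size section itself allows 2% drop-out: 0.02 × 108 = 2.16 children. Some missing values are near certain, so read literally GEE becomes the longitudinal method.

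**2. Why the methods differ.** Take a separate mean for each arm and time. Independence GEE solves Σ R(Y − μ) = 0 at 48 hours, where R = 1 if the reading exists. The estimate of μ is then the mean of the readings that exist, which is right only if R is unrelated to Y within arm. Likelihood also uses the regression of the 48-hour value on earlier readings, so loss that depends on those earlier readings is allowed for.

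**3. Size under assumed inputs.** The documents give no figure for the amount or cause of missing urine, so everything here is illustrative.

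*First simulation:* 54 per arm, 4 visits, true effect -0.5 SD, removal depending on the last observed value, 42-69% missing at 48 hours, 400 runs per setting. Ratio of estimated to true 48-hour effect:
- independence GEE: 0.84-0.89 (weak dependence) and 0.61-0.75 (moderate), that is, 11-16% and 25-39% too small;
- exchangeable GEE: 0.94-1.01;
- maximum likelihood: 0.94-1.02.

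*Second simulation:* 200,000 per arm to show large-sample bias; baseline, 6, 12, 24 and 48 hours; SD 1; correlation 0.7 (AR(1) or exchangeable). Samples are lost for good after 6 hours, more often at lower (better) values, with log-odds slope 1. Where removal differs by arm, it is more frequent under treatment by 0.8 on the log-odds scale. MNAR (missing not at random) means loss depends on the value that is itself not seen. Bias in the 48-hour contrast, in SD units, over both correlation structures:

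| Loss | True effect | Removal process | GEE, independence | GEE, exchangeable or AR(1) | Likelihood, unstructured |
|---|---|---|---|---|---|
| MAR | 0 | same | about 0 | about 0 | about 0 |
| MAR | -0.5 | same | 0.075 to 0.082 | 0.003 to 0.020 | 0.002 to 0.007 |
| MAR | 0 | differs by arm | 0.145 to 0.184 | 0.000 to 0.057 | 0.001 to 0.004 |
| MAR | -0.5 | differs by arm | 0.218 to 0.280 | -0.008 to 0.074 | 0.000 to 0.003 |
| MNAR | 0 | same | about 0 | about 0 | about 0 |
| MNAR | -0.5 | same | 0.116 to 0.132 | 0.044 to 0.083 | 0.054 to 0.072 |
| MNAR | 0 | differs by arm | 0.211 to 0.224 | 0.068 to 0.144 | 0.087 to 0.138 |
| MNAR | -0.5 | differs by arm | 0.348 to 0.369 | 0.104 to 0.228 | 0.130 to 0.236 |

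As a share of the 0.5 SD effect, independence GEE under MAR loses 0.075/0.5 = 15% to 0.082/0.5 = 16% with the same process, and 0.218/0.5 = 44% to 0.280/0.5 = 56% when removal differs by arm.

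**4. Change of estimand.** With a random intercept of standard deviation σ, the population-average log odds ratio is about 1/√(1 + 0.346σ²) of the subject-specific one. For σ = 1: 1/√1.346 = 0.86. For σ = 2: 1/√2.384 = 0.65. Both σ values are assumed.

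**5. Sample size.** The plan's 108 does not depend on this point. It reproduces: with 0.71 versus 0.57 mg/kg and SDs 0.3 and 0.2, an unequal-variance t-test needs 54 per arm (power 80.6%; 79.9% at 53).

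**The case against.** Several objections have force.

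- *The bias figures rest on independence working correlation, which the plan does not name.* This stands. The plan's remark on autocorrelation, though attached to the mixed model, makes independence the less natural choice. For a continuous outcome, GEE and a Gaussian mixed model with the same covariance solve the same equations for the means, so the covariance matters more than the label. But the plan fixes no working correlation for GEE.
- *The missingness mechanism is inferred.* This stands. The documents do not say when or why the Foley is removed, and three of the four places that schedule urine carry no catheter condition.
- *The biomarkers are assayed only at the end of the study.* Staff cannot act on values they have not seen. Any link with removal must run through clinical status, which earlier biomarker readings may not capture. The loss may then be MNAR, and the table shows likelihood biased as well, by about as much as correlated GEE. This stands and limits what the fix can achieve.
- *The text does not expressly say that GEE replaces the mixed model.* True, but replacement is the natural reading, and nothing describes the two being run together.

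A reader might infer that the Foley rule creates recovery-related missingness and that the switch therefore biases the longitudinal comparison toward no effect. The documents do not support that. They do not link catheter removal to recovery, and bias in the contrast depends on the mechanism, the working correlation, and whether outcome or removal differs by arm.

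**Conclusion.** The rule should be changed. It points the wrong way under MAR and leaves the estimand for logit-link outcomes to chance; neither conclusion depends on the simulations. The size of any bias in this trial is unknown. The 11-39% understatement holds for independence GEE, a true effect of -0.5 SD and 42-69% of 48-hour samples missing, all assumed.

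The reach is limited. The affected analysis is secondary and descriptive. The Foley condition is attached to urine samples, hence NGAL, WNT4 and superoxide dismutase (possibly also urine output and the urine-output limb of AKIN), and not to troponin, creatinine, pain, opiate use or inotropic score. The three biomarkers are not named in the objectives. The 48-hour change t-test is untouched by the GEE sentence, but it has no missing-data rule of its own and is at least as exposed for these biomarkers.

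**What to change.** - Delete the GEE sentence. Fit the planned mixed model by maximum likelihood to all available readings, whether or not any are missing, with treatment by time.
- Name the covariance in advance: unstructured for the short urine schedule, or a continuous-time structure, because 6, 12, 24 and 48 hours are unequally spaced. Unstructured suits five urine times including baseline (5 × 6/2 = 15 parameters) but not 24 pain readings (24 × 25/2 = 300), which need a stated parametric structure.
- For logit-link outcomes, state once whether the subject-specific or population-average odds ratio is wanted, and keep to it.
- If GEE is kept, use inverse-probability weighting or multiple imputation and name the working correlation.
- State the missingness assumption and add an MNAR sensitivity analysis for the urine outcomes, for example shifting the unobserved values by a prespecified range in each arm.
- Reconcile the catheter condition and 6-hourly sampling in Study Design with the fixed times in the PICU section, the Documentation Guide and Appendix B. Record the time sampling ended for each child.

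The cost is a few sentences and one sensitivity analysis. The mixed model is already planned and the sample size does not change.
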